## 3 OBJECTIVES AND ENDPOINTS

Note: Clinical endpoints are gathered from information collected as part of the participants' routine care. No study specific procedures will be performed.

Objectives	Endpoints
Primary Safety	

 
• To assess the incidence of symptomatic venous thrombosis (VT) in patients with PowerPICC, PowerPICC SOLO2, and PowerGroshong PICC devices (PICCs) used for both short- and long-term venous access.
 
	
 
• Incidence defined as any new occurrence of symptomatic VT defined by thrombus presence by ultrasonography or other imaging
 

Primary Performance	
• To assess the rate of therapy completion in PICCs used for both short- and long-term therapy.	• Percent of PICCs that remain in place through the required therapy time period (completion of therapy) (success/failure)
Secondary Safety	
• To assess the incidence of select complications during catheter insertion and while the catheter is in-situ in patients with PICCs used for both short- and long-term venous access.	
 
• Incidence defined as any new occurrence of: 
 
○ Phlebitis – inflammation of the cannulated vessel identified by redness, swelling, warmth, tenderness, and/or cord formation
 
○ Extravasation – accidental infiltration of a vesicant or chemotherapeutic drug into the tissue around the catheter
 
○ Local infection - presence of pus at the exit site and/or culture confirmed site infection
 
○ Catheter-related bloodstream infection - positive blood culture(s) with a microorganism not related to another source (e.g., UTI) OR positive blood culture(s) with microorganism matching catheter tip culture OR blood cultures from peripheral venous puncture and PICC positive with the same microorganism
 
○ Accidental dislodgement – catheter accidentally dislodged the extent to which it requires replacement
 
○ Vessel laceration – a tear in the tissue of the vessel
 
○ Vessel perforation – a hole formed in the vessel
 
 
 

Secondary Performance	

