### **7.4.1 Use and Maintenance Data**

Device assessments will be conducted as part of the participant's routine medical care. Information from these assessments about the use and maintenance of the PICC will be documented, including, but not limited to:

- Catheter patency
- Performance of catheter/site maintenance procedures
- Type of use (i.e., IV therapy (e.g., antimicrobial, TPN, blood products), blood sampling, CVP monitoring, injection of contrast media)

- Adverse events/complications (including but not limited to study endpoints such as extravasation, VT, phlebitis, infection, etc.)
- Device deficiencies/failures (including but not limited to accidental dislodgement and occlusion)

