## 9 ADVERSE EVENTS AND DEVICE DEFICIENCIES

### 9.1 Definitions of Events

#### 9.1.1 Adverse Events (AEs)

An AE is defined as any untoward medical occurrence, unintended disease or injury, or untoward clinical signs (including abnormal laboratory findings) in subjects, users or other persons, whether or not related to the investigational medical device. In this study, AE collection will be limited to those occurring in the arm in which the device is inserted or upper torso, as well as any other undesirable clinical event judged to be related or likely related to the PowerPICC device or the suture or stabilization method used for securement of the device, regardless of anatomical region, that in the opinion of the investigator warrants reporting.

Pre-existing conditions should be considered as part of the participant's medical history and should not be reported as an AE unless there is a substantial increase in severity or frequency of the condition, which has not been attributed to natural history. Exacerbation of an existing condition should be reported as an AE if the event meets the protocol definition of an AE.

The clinical course of the event will be followed according to accepted standards of medical practice until the event resolves, stabilizes, or in the opinion of the Investigator, is no longer considered clinically significant. The Investigator must supply the Sponsor with information concerning the follow up and/or resolution of the AE.

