## 9.6 Device Deficiencies

The Investigator will record, without unjustified delay, a device deficiency if a device used failed to meet its performance specifications whether due to mechanical failure, malfunction, or defect. Device deficiencies also include use errors and inadequate labeling. This applies to: devices used to treat the participant, or devices in which the package was opened, but the device was not used for treatment, or devices with which treatment was attempted, but the device did not remain through the entire study period.

All mechanical failures, malfunctions, missing components, and defects of the study devices will be recorded on the appropriate Case Report Form and will be promptly reported to the Sponsor. The device(s) should be returned to the Sponsor if requested.

If the device deficiency was associated with an AE, the reporting provisions for AEs, ADEs, SAEs, SADEs and UADEs/USADEs apply.

Reported deficiencies will be investigated and reported as required by appropriate national laws and regulations. The site may be contacted to provide additional information to allow the Sponsor to conduct a thorough investigation.

It is the responsibility of the Investigator, or their designee, to notify the IRB/EC of such device deficiencies in accordance with the IRB/EC and/or local regulations.

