4.4.2 Analysis of Secondary Safety Variables

Complications

For each complication listed as a secondary endpoint, the incidence will be calculated by dividing the number of participants experiencing the event by the total number of participants with non-missing data on the corresponding complication in the safety set and displayed using frequency tables. 95% confidence interval for the incidence will be additionally presented.

The following complications will be analyzed:

- Phlebitis (Preferred term (PT): "Catheter site phlebitis" / Lower level term (LLT): "Catheter site phlebitis")
- Extravasation (PT: "Catheter site extravasation" / LLT: "Catheter site extravasation")
- Local infection (as ticked on the adverse event (AE) case report form (CRF) page)
- Catheter-related bloodstream infection (as ticked on the AE CRF page)
- Accidental dislodgement (System organ class (SOC): "Product issues" / PT: "Device dislocation" / LLT: "Catheter dislodgment")
- Vessel laceration (as recorded on the catheter insertion CRF page)
- Vessel perforation (as recorded on the catheter insertion CRF page)

For local infections additionally the number of participants with local infections confirmed according to protocol (presence of pus at the exit site and/or culture confirmed site infection) by type of device and overall will be displayed in a footnote.

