4.4.3 Further Safety Variables

Adverse events (AEs)

AEs will be coded by using the Medical dictionary for regulatory activities version 23.0 (MedDRA).

AEs will be tabulated by SOC and PT (MedDRA). The number of entries, as well as the number and rate of affected participants will be reported for each type of device. Additionally, AEs will be presented by severity.

SAEs, non-serious AEs, and AEs which are related to device (adverse device effects [ADEs]), SADEs, AEs which are related to procedure, or related to accessories will be presented separately.

All AEs will be listed together with study day of AE (start date of AE – insertion date) as well as duration of AE for AEs with complete dates.

AEs are considered being related to device/procedure/accessories, if relationship is at least likely or relationship assessment is missing.

Device deficiencies

Details regarding device deficiencies will be listed.

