4.3.2 Device Deficiencies

- Listing 4.3.2.1: Device Deficiencies

Safety Set

Variables: Type of Device, Participant + all variables on device deficiency-form, Evaluable Set (yes/no)

Note: Type of devices will be displayed as “by-variable” within a subtitle.

5 Performance Analysis

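### SAP 4.4.2 counts accidental dislodgement and local infection by rules that need not match the protocol endpoints, and SAP Section 5 declares only the denominator change

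*SAP*

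**What the plan says.** **Protocol definitions.** Section 3 defines accidental dislodgement as "catheter accidentally dislodged the extent to which it requires replacement". It defines local infection by pus at the exit site, culture confirmation, or both. Protocol 10.5 asks, for each complication, for participants with the event divided by all participants, with 95% intervals where appropriate.

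**Protocol data sources.** Section 7.4.1 has two relevant bullets. One reads "Adverse events/complications (including but not limited to study endpoints such as extravasation, VT, phlebitis, infection, etc". The other, which names dislodgement, reads "Device deficiencies/failures (including but not limited to accidental dislodgement and occlusion". Section 9.6 links the two routes conditionally: "If the device deficiency was associated with an AE, the reporting provisions for AEs, ADEs, SAEs, SADEs and UADEs/USADEs apply".

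**SAP derivations.** Section 4.4.2 identifies dislodgement as "Accidental dislodgement (System organ class (SOC): 'Product issues' / PT: 'Device dislocation' / LLT: 'Catheter dislodgment". Local infection is whatever is ticked on the adverse event CRF page. Protocol-confirmed infections are to be counted, by device type and overall, in a footnote to Table 4.2.1.1. For deficiencies, SAP 4.4.3 says "Details regarding device deficiencies will be listed", and Listing 4.3.2.1 prints "all variables on device deficiency-form".

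**Declared changes.** SAP Section 5 names one change from the protocol: denominators are restricted to participants with non-missing data.

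**The concern.** Both events are named secondary safety endpoints. The SAP plans no inferential assessment, so the descriptive rates and their intervals are the safety result. If a numerator does not follow the endpoint definition, the printed rate belongs to something else.

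For dislodgement, the mismatch can run in either direction. An event filed only as a deficiency is not coded and does not reach the endpoint table. A coded event that needed no replacement is counted although the protocol would exclude it.

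For local infection, the row and its interval describe a broader count than the protocol's. The protocol-defined count gets no planned participant-based rate and no interval.

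**Working it through.** **Stated figures.** The point disputes none of the plan's numbers, and they reproduce. With n = 150 and a 10% rate, the half-width is 1.96 × √(0.10 × 0.90 / 150) = 4.80 points (stated 4.8%). The chance of at least one event is 1 − 0.99^150 = 77.9% (stated 78%) and 1 − 0.98^150 = 95.2% (stated 95%).

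**Dislodgement, step by step.**

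1. *Condition.* The protocol requires that the catheter needs replacing. The SOC/PT/LLT string in SAP 4.4.2 carries no such condition.
2. *Source.* The SAP describes MedDRA coding for adverse events only. Protocol 7.4.1 names dislodgement in the deficiency bullet. Section 9.6 brings a deficiency into adverse event reporting only when it is associated with an adverse event.
3. *Does any rule force an adverse event entry?* Section 9.1.1 collects events in the arm or upper torso. It also collects other events related to the device or its securement, but only those "that in the opinion of the investigator warrants reporting". No text requires an entry for a dislodgement without harm.
4. *Other routes.* Listing 3.7 has yes/no experience items for five complications, and dislodgement is not among them. Reason for removal appears in Table 3.5 (evaluable set) and Listing 3.6 (safety set), but neither feeds the endpoint table. The data-review list in SAP 4.9 is open-ended. It names successful placement and receipt of treatment, but no reconciliation of adverse event, deficiency and removal records.

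**Local infection, step by step.**

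1. The SAP plans a separate count of protocol-confirmed cases, so it allows that ticked and confirmed cases may differ.
2. The percentage and interval in Table 4.2.1.1 come from the tick.
3. The footnote shell has the form a/b, with b undefined. It reads as confirmed out of ticked infections, not as an incidence over participants.

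**Size.** The documents give no event counts, so the counts below are assumptions. Each participant moves a rate by 1/150 = 0.67 points for one device type, or 1/450 = 0.22 points overall.

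The SAP's interval is Clopper-Pearson. The lower limit is the 2.5% quantile of Beta(x, n − x + 1), and the upper limit is the 97.5% quantile of Beta(x + 1, n − x). For x = 0 the lower limit is 0. With n = 150:

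| Events (assumed) | Rate | Exact 95% CI |
|---|---|---|
| 0 | 0.0% | 0 to 2.4% |
| 2 | 1.3% | 0.2 to 4.7% |
| 3 | 2.0% | 0.4 to 5.7% |
| 4 | 2.7% | 0.7 to 6.7% |
| 6 | 4.0% | 1.5 to 8.5% |

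- *Dislodgement, 3 protocol-defined events (2.0%).* If one is recorded only as a deficiency, the table shows 1.3%. If instead one extra coded event needed no replacement, it shows 2.7%. If both happen, it shows 2.0% again and the errors cancel.
- *Local infection, 6 ticked (printed as 4.0%).* The protocol-defined rate is 4.0% if all 6 are confirmed, 2.0% if 3 are, and 0% if none is.

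**The case against.** The strongest reply on dislodgement is that the gap may never open.

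- Both bullets in Protocol 7.4.1 are open-ended and do not assign events to forms. Dislodgement is itself a study endpoint, so the adverse event bullet can be read to cover it.
- In Section 9.1.1 the investigator's discretion most naturally attaches to the second group of events, not to those in the arm.
- Losing a catheter and needing another is readily an untoward occurrence, so a truly harmless dislodgement mostly falls outside the endpoint anyway.
- The choice of a product-issue term suggests that the authors expected dislodgements on the adverse event page.
- Listings 3.6, 4.3.1.1 and 4.3.2.1 are all on the safety set, so the material for a cross-check is already planned.

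On local infection, the SAP does commit to a count of participants with confirmed infection, by device type and overall. A reader could work out the rate and interval from it. What is left there is largely presentation.

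Much of this stands. The CRFs and the data validation plan were not supplied, many dislodgements may well be filed as adverse events, and the footnote softens the second part. But none of it supplies a rule that brings a deficiency-only dislodgement into the numerator or removes a coded event that needed no replacement. Listings that would allow a cross-check do not make one happen. Nor does the review of missing endpoint data in SAP 4.7 amount to reconciling sources. Dislodgement has no equivalent of the local-infection footnote.

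**Conclusion.** The concern holds. As written, SAP 4.4.2 can report a rate for something other than the protocol endpoint in both cases, and Section 5 does not say so. The documents show that a mismatch is possible, not that one will occur. Its size is unknown and may be zero.

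The dislodgement rate could be too high, too low or unchanged. The local-infection row should be at or above the protocol-defined rate, provided confirmed cases are a subset of ticked ones. The effect is confined to two secondary descriptive rates. Sample size, error rates and the primary endpoints are untouched. Confidence is medium, because CRF wording or completion instructions could narrow the gap.

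**What to change.** 1. **Dislodgement.** Count a participant once if an event meeting the protocol definition is recorded on the adverse event form, on the deficiency form or as the reason for removal. Add this reconciliation, including the replacement condition, to the data-review items in SAP 4.9. If the data validation plan already contains it, cite that plan.
2. **Local infection.** Give protocol-confirmed cases their own row in Table 4.2.1.1, over safety-set participants with non-missing data, with a Clopper-Pearson interval. Keep the ticked count as supportive.
3. **If the present derivations are kept.** Declare both numerator changes in SAP Section 5 and define b in the footnote.
4. **Optional.** Compare the coded phlebitis and extravasation terms with the corresponding items in Listing 3.7. No error is shown there.

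The cost is SAP wording, one table row, and minor programming and data review. The listings suggest that most of the data exist. However, none names a replacement-needed variable, and the removal-reason categories are shown only in part, so the CRFs must be checked before the derivation is fixed.

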4.4.3 Further Safety Variables

Adverse events (AEs)

AEs will be coded by using the Medical dictionary for regulatory activities version 23.0 (MedDRA).

AEs will be tabulated by SOC and PT (MedDRA). The number of entries, as well as the number and rate of affected participants will be reported for each type of device. Additionally, AEs will be presented by severity.

SAEs, non-serious AEs, and AEs which are related to device (adverse device effects [ADEs]), SADEs, AEs which are related to procedure, or related to accessories will be presented separately.

All AEs will be listed together with study day of AE (start date of AE – insertion date) as well as duration of AE for AEs with complete dates.

AEs are considered being related to device/procedure/accessories, if relationship is at least likely or relationship assessment is missing.

Device deficiencies

Details regarding device deficiencies will be listed.

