Study Devices	
The full range of CE-marked devices marketed in the EU will be available for use in this study. These devices include:
 

• PowerPICC

• PowerPICC SV (Small Vein)

• PowerPICC FT (Fit for Veins)

• PowerPICC HF (High Flow)

• PowerPICC SOLO2,

• PowerPICC SOLO2 FT

• PowerPICC SOLO2 HF

• PowerGroshong PICC Catheters

• Accessory Guidewires

• Accessory Stylets

 
PowerPICC, PowerPICC SOLO2, and PowerGroshong PICC devices are intended for both short- (<30 days) and long-term (<math>\geq 30</math> days) peripheral access to the central venous system for intravenous (IV) therapy, blood sampling, infusion, or therapy, and power injection of contrast media. PowerPICC and PowerPICC SOLO2 catheters may also be used for central venous pressure measurements.
 
Guidewires and Stylets: Guidewires and Stylets must retain integrity within the vasculature system and facilitate placement of the catheter.
 
All devices used in this study will be used in a manner consistent with their labelled indications.

Protocol Title	Prospective Observational Study of the Power PICC Family of Devices and Accessories

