### **9.1.3 Adverse Device Effect (ADE) / Serious Adverse Device Effect (SADE)**

An adverse device effect is defined as any adverse event that is considered to be related to the use of an investigational medical device. This definition includes any event resulting from insufficiencies or inadequacies in the instructions for use, deployment, implantation, or operation or any malfunction of the investigational device (study device) and includes any event that is a result of a user error.

A serious adverse device effect (SADE) is defined as an ADE that has resulted in any of the consequences characteristic of an SAE.

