### 9.3 Relationship of Adverse Event to Device(s)/Procedure

Each AE will be assessed for its relationship to the study device or procedure according to the following guidelines.

- A. Assess each AE for its relationship to the device or procedure.
- Device Related: This category should be restricted to AEs directly attributable to the study device used.
  - Procedure: A procedure includes any activity performed with the study device
- B. The following categories shall be used for assigning the certainty of the relatedness.

Relatedness	Description
Not Related	Event is independent of study intervention and/or evidence exists that the event is related to another etiology. There must be an alternative etiology documented by the clinician.
Unlikely Related	Event in which the temporal relationship to study intervention makes a causal relationship improbable (e.g., the event did not occur within a reasonable time of the study device use) and in which underlying disease provides plausible explanations (e.g., the participant's clinical condition other concomitant treatments).
Likely Related	Event in which there is evidence to suggest a causal relationship and the influence of other factors is less likely. The event occurs within a reasonable time after use of the study device and is less likely to be attributed to concurrent disease.
Related	Event in which there is clear evidence to suggest a causal relationship and other possible contributing factors can be ruled out. The event occurs in a plausible time relationship to use of the study device and cannot be explained by concurrent disease.

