Footnote 1: Each participant is counted at most once for the line total. MedDRA version <xx.x> was used for coding.

- Table 4.3.1.4: Serious AEs by System Organ Class

Safety Set

Note: The same table layout as used for table AEs by system organ class will be used. Only serious AEs will be tabulated.

Footnote 1: Adverse events documented as serious on the AE form are tabulated.

Footnote 2: Each participant is counted at most once for the line total. MedDRA version <xx.x> was used for coding.

- Table 4.3.1.5: Non-serious AEs by System Organ Class

Safety Set

Note: The same table layout as used for table AEs by system organ class will be used. Only non-serious AEs will be tabulated.

Footnote 1: Adverse events documented as non-serious on the AE form are tabulated.

Footnote 2: Each participant is counted at most once for the line total. MedDRA version <xx.x> was used for coding.

- Table 4.3.1.6: Adverse Device Effects by System Organ Class

Safety Set

Note: The same table layout as used for table AEs by system organ class will be used.

Footnote 1: Adverse events documented as related to device on the AE form are tabulated.

Footnote 2: Each participant is counted at most once for the line total. MedDRA version <xx.x> was used for coding.

- Table 4.3.1.7: Serious Adverse Device Effects by System Organ Class

Safety Set

Note: The same table layout as used for table AEs by system organ class will be used. Only serious AEs will be tabulated.

Footnote 1: Serious adverse events documented as related to device on the AE form are tabulated.

Footnote 2: Each participant is counted at most once for the line total. MedDRA version <xx.x> was used for coding.

- Table 4.3.1.8: AEs Related to Procedure by System Organ Class

Safety Set

Note: The same table layout as used for table AEs by system organ class will be used. Only AEs related to procedure will be tabulated.

Footnote 1: Adverse events documented as related to procedure on the AE form are tabulated.

Footnote 2: Each participant is counted at most once for the line total. MedDRA version <xx.x> was used for coding.

- Table 4.3.1.9: AEs Related to Accessories by System Organ Class

Safety Set

Note: The same table layout as used for table AEs by system organ class will be used. Only AEs related to Accessories will be tabulated.

Footnote 1: Adverse events documented as related to accessories on the AE form are tabulated.

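### The SAP builds ADE and SADE counts from device-relatedness alone, a narrower scope than the protocol's definition, and does not declare the change

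*SAP*

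**What the plan says.** **Protocol.** Section 9.1.3 sets the scope by use: "An adverse device effect is defined as any adverse event that is considered to be related to the use of an investigational medical device". It goes on to include "any event resulting from insufficiencies or inadequacies in the instructions for use, deployment, implantation, or operation or any malfunction of the investigational device", and adds that the definition "includes any event that is a result of a user error". A SADE is the serious subset, so it has the same scope. The study-device list in the synopsis (section 1.1) names "Accessory Guidewires" and accessory stylets alongside the catheters.

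Section 9.3 has the investigator rate each AE against the device or the procedure. Of the device rating it says: "This category should be restricted to AEs directly attributable to the study device used". The procedure rating covers anything done with the study device.

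**SAP.** Section 4.4.3 states that "AEs which are related to device (adverse device effects [ADEs]), SADEs, AEs which are related to procedure, or related to accessories will be presented separately". It counts a relationship as present when it is at least likely or when the assessment is missing, and applies this rule equally to device, procedure and accessories. In Appendix A, the footnote to Table 4.3.1.6 (ADEs) reads "Adverse events documented as related to device on the AE form are tabulated", and Table 4.3.1.7 (SADEs) uses the same rule for serious events. Procedure-related and accessory-related AEs go to Tables 4.3.1.8 and 4.3.1.9. Section 5, on changes from the protocol, lists only the change of denominator to participants with non-missing data.

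**The concern.** ADE and SADE are defined terms in the protocol, and a reader of the final tables will assume they carry that meaning. In the SAP they mean something narrower. An investigator who follows Protocol 9.3 can correctly rate an implantation or user-error event as procedure-related and not device-related. Under 9.1.3 that event is an ADE, but under SAP 4.4.3 it is not. The same applies to an event rated related only to a guidewire or stylet.

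At stake is whether the ADE and SADE lines of the report match the protocol. Sites also report SADEs to the sponsor during the study under Protocol 9.4, using the protocol's definition, so the final SADE table could disagree with the SADEs reported along the way.

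**Working it through.** **The plan's own figures.** The plan states no expected ADE or SADE rate. Its only related figures are the sample-size statements (Protocol 10.2, SAP 1.2) for n = 150 per device type, and all three reproduce:

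- Half-width at a 10% rate: 1.96 × √(0.10 × 0.90 / 150) = 4.8%.
- Chance of at least one event at a 1% rate: 1 − 0.99^150 = 77.9% (stated 78%).
- Chance of at least one event at a 2% rate: 1 − 0.98^150 = 95.2% (stated 95%).

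None of them depends on how an ADE is defined.

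**Step 1: compare the scopes.**

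| AE rated at least likely related to | ADE under Protocol 9.1.3? | ADE under SAP 4.4.3? |
|---|---|---|
| the device | yes | yes |
| the procedure, not the device | yes: arises from use, implantation or operation | no |
| a guidewire or stylet, not the device | yes: these are listed study devices | no |

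**Step 2: direction.** Let D, P and A be the sets of AEs counted as related to the device, the procedure and the accessory guidewires/stylets, with the same threshold and missing-data rule for each. The SAP's ADE set is D; the protocol's is D ∪ P ∪ A. Since D lies inside the union, the SAP count is at most the protocol count. It is lower as soon as one AE falls in P or A but not in D. The same holds among serious AEs, and so for SADEs.

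**Step 3: can the planned tables recover the protocol counts?** Table 4.3.1.1 has separate rows for ADEs, procedure-related AEs and accessory-related AEs. If n_D, n_P and n_A participants fall in those rows, the union lies between max(n_D, n_P, n_A) and n_D + n_P + n_A, assuming the accessory row refers to guidewires and stylets. The exact figure needs the overlaps, which are not tabulated. For SADEs, procedure- and accessory-related AEs are not split by seriousness. Table 4.3.1.1 therefore shows only that the protocol-defined count lies between its SADE row and its SAE row. Exact figures would have to be worked out from the AE listings.

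**Step 4: range of sizes (assumed values).** Let d be the share of participants with a device-rated ADE, and x the share whose only qualifying AE is rated procedure- or accessory-related. The protocol-defined rate is d + x, and the share of ADE participants left out is x / (d + x).

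| x | d = 5%: rate; share left out | d = 10%: rate; share left out |
|---|---|---|
| 0% | 5%; 0% | 10%; 0% |
| 1% | 6%; 17% | 11%; 9% |
| 2% | 7%; 29% | 12%; 17% |
| 5% | 10%; 50% | 15%; 33% |

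At x = 1%, the chance that at least one participant is left out is 1 − 0.99^150 = 77.9% for one device type and 1 − 0.99^450 = 98.9% for all 450. Neither d nor x is given in the documents.

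**The case against.** The strongest reply is that this is a labelling mismatch in a descriptive output and that no event is hidden. Most of that stands:

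- AEs are further safety variables in the SAP. The primary safety variable is symptomatic VT and the secondary ones are seven named complications. The ADE tables carry no confidence intervals, and no sample-size statement rests on them. A reader might infer that the study's main safety result is biased; the documents do not support that.
- A reader might infer that insertion injuries disappear. They do not. Vessel laceration and perforation come from the insertion CRF page whatever the relatedness rating, and Table 4.2.1.1 gives them with confidence intervals. Serious AEs are in Table 4.3.1.4 and the listings, procedure- and accessory-related AEs sit beside the ADE row in Table 4.3.1.1, and device deficiencies, which include use errors, are listed.
- A reader might infer that the rates are certainly too low. Nothing in Protocol 9.3 or SAP 4.4.3 makes the ratings mutually exclusive, so an investigator may mark both device and procedure, and then nothing is left out. The AE form is not in the documents, so the frequency of procedure-only or accessory-only ratings is unknown.
- A reader might infer from the footnotes that AEs with missing relatedness are excluded. SAP 4.4.3 states that they count as related, and the footnotes read naturally as naming the source field. This is a matter of aligning the wording.
- The term accessories is not defined for the AE form. If sites used it for other tray contents (Protocol 6.3), adding the whole category would go beyond the study-device list.

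The reply does not supply a protocol-defined SADE count or a deduplicated ADE count in any planned table, and it does not explain why SAP section 5 omits the narrower scope.

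**Conclusion.** The inconsistency is real and worth correcting before the final tables, but its consequence is limited. The SAP's ADE and SADE counts can be equal to or lower than those under Protocol 9.1.3. They are lower only if at least one AE is rated at least likely related to the procedure or to a guidewire or stylet, and not to the device. The size cannot be computed from the documents; the percentages under the working are illustrations and include zero.

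The conclusion rests on two readings. The first is that the procedure rating in Protocol 9.3 describes use of the device in the sense of 9.1.3. The second is that guidewires and stylets fall within the ADE definition because the synopsis lists them as study devices, although 9.1.3 does not name them. The procedure gap stands without the second reading.

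**What to change.** In SAP 4.4.3, define an ADE as any AE at least likely related, or with missing relatedness, to the device, the procedure, or the accessory guidewires and stylets listed as study devices. Define a SADE as its serious subset. Build Tables 4.3.1.1, 4.3.1.6 and 4.3.1.7 on that flag. Keep the device-, procedure- and accessory-related tables as a breakdown, each with a serious count, and align the footnotes with the missing-relatedness rule.

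If the narrow scope is intended, the minimum is to relabel the ADE and SADE tables as device-related AEs and device-related serious AEs, and to declare the departure in SAP section 5.

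The cost is wording in the SAP and Appendix A plus one derived variable from relatedness ratings the tables already use. If the accessories field does not separate guidewires and stylets from other tray items, those AEs need a check at data review. Reported ADE and SADE rates may come out somewhat higher.
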